7.2.2.2. Dose-Escalation Method

Adaptive scheme, with incorporation of a Bayesian model-based, toxicity-band method (Neuenschwander et al. 2008), will be used to assess the safety of LY2510924 given in combination with durvalumab. The Bayesian model-based, toxicity-band method incorporates the prior expectations of the dose-toxicity curve and the observed DLT data after each cohort and provides quantitative guidance on the determination of the dose level for the next cohort. The dose recommendation relies on maximizing the probability of targeted toxicity while controlling the probability of excessive or unacceptable toxicity. This method will be applied to the observed data on an ongoing basis throughout the dose escalation. The toxicity-band method will stop early if the prespecified maximum number of patients is reached or the recommended next dose level has been administered to at least 6 patients.

During the dose-escalation period, the investigators and Lilly CRP or designee in consultation with collaborator will consider the model recommendation, the observed DLT rate, and any

DLT-equivalent toxicities observed in Cycle 2 and beyond at each cohort to determine the next dose level and determine when to stop dose escalation. Safety data, in particular, DLTs, will be the primary criteria for dose escalation. In addition, if available at the time of the dose-escalation decision, PK results will be used as secondary/supporting data for dose escalation. Additional patients may, therefore, be enrolled at a specific dose level to characterize PK/pharmacodynamics. No dose escalation can occur without prior discussion and agreement between the investigator and the Lilly CRP or designee in consultation with collaborator; the decision will be documented in writing.

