7.2.4. DLT-Equivalent Toxicity

A DLT-equivalent toxicity is defined as an AE occurring during Cycle 2 and beyond in Phase 1a that would have met the criteria for a DLT if it had occurred during Cycle 1 or during any cycle in Phase 1b. The DLT-observation period will be extended to Cycle 2 if a DLT-equivalent toxicity is observed during Cycle 2 in any cohort in Phase 1a. For individual patients experiencing a DLT-equivalent toxicity, dose adjustments will be made as outlined in Section 7.2.5. At each interim analysis (as defined in Section 10.10), the rate of DLT-equivalent toxicities will be assessed. If the rate of DLT-equivalent toxicities is unacceptable (for example, a DLT-equivalent toxicity is observed in >33% patients at a given dose level), the data will be reviewed by study investigators and the Lilly CRP or designee in consultation with collaborator and a safety analysis may be triggered. If the findings indicate that a dose level does not have an acceptable safety profile for chronic (Cycle 2 or later) administration, then a lower dose level will be chosen for further investigation. This decision will be documented in writing.

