Babb et al. (1998) proposed the Escalation with Overdose Control (EWOC) method that directly controls the probability of overdosing during dose escalation. EWOC is also a CRM-type method. During the escalation, EWOC selects the next dose such that the predicted probability that the new dose exceeds the MTD is equal to a prespecified feasibility bound $\alpha=0.25$. The connection between CRM and EWOC is that CRM typically uses the middle (mean or median) of the MTD's posterior distribution as the next recommended dose, whereas EWOC uses the 25th percentile. Therefore, EWOC is a more conservative method than the original CRM method.

Toxicity-Band Design

Neuenschwander et al. (2008) extended the concept of EWOC (Babb et al. 1998) and proposed considering the uncertainty of the posterior distributions and using interval estimates to make the dose recommendation, herein referred to as the toxicity-band design.

The Model

A two-parameter logistic model is used to model the relationship between dose and probability of a DLT:

$$\text{logit}\{p(d)\} = \alpha + \beta \log\left(\frac{d}{d^*}\right), \quad \beta > 0. \quad (1.1)$$

In the model, d is the true dose and $p(d)$ is the probability of a DLT at dose d . d^* is the reference dose such that α is interpreted as the log-odds of a DLT at d^* .

Toxicity Band

The probability of a DLT is categorized to 4 bands:

- Underdosing: $p(d)$ in $(0, 0.20]$
- Targeted toxicity: $p(d)$ in $(0.20, 0.33]$
- Excessive toxicity: $p(d)$ in $(0.33, 0.60]$
- Unacceptable toxicity: $p(d)$ in $(0.60, 1.00]$

Overdosing is defined as $p(d) > 0.33$.

Dose Recommendation

During the escalation, after each cohort of patients, we

1. Calculate the posterior probabilities of the 4 toxicity bands, for each dose.
2. Exclude the doses such that the posterior probabilities of overdosing are larger than 0.25 (overdosing control criteria). The remaining doses are the ones that satisfy the overdose control criteria.
3. Among the remaining doses, the dose with the highest posterior probability in the targeted toxicity band will be the model recommendation of the next dose.

The data will be evaluated on an ongoing basis until the MTD is determined. Once the MTD has been identified, a discussion between the sponsor and investigators may occur in order to treat additional patients at intermediate doses below the MTD.

Dose Range and Reference Dose

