Assuming that the starting dose level is 20 mg, based on the preclinical data, the highest dose level that will be explored in this study is 40 mg and the reference dose in model (1.1) is chosen as $d^* = 40$ mg.

The Prior Distribution on Model Parameters

A Quantile-based uninformative prior (Neuenschwander et al. 2008) is used to derive a bivariate-normal prior on $(\alpha, \log\beta)$. Based on preclinical experience of LY2510924, the prior median probability of DLT for the dose levels was determined as in Table App.1. Any intermediate dose level within the starting doses to 40 mg can be explored.

Table App.1. Prior Median Probability of Dose Limiting Toxicity at Each Dose Level

Dose (mg)	Median Probability of Dose Limiting Toxicity
10	0.06
20	0.12
30	0.18
40	0.26

For each dose, the minimally informative unimode Beta distribution (a,b) is derived as the prior distribution for the probability of DLT, so that the operating characteristics of the model are robust to the selected prior distribution of DLT:

- For median probability of DLT <0.5 , $b=1$ and $a(<1)$ are tuned to match the median.
- For median probability of DLT >0.5 , $a=1$ and $b(<1)$ are tuned to match the median.

Figure App.1 shows the median and the 95% confidence interval (CI) of the prior distribution of the DLT rate at each dose level.

[figure not shown]

Figure App.1. The prior distribution of the dose limiting toxicity rate at each dose level.

A bivariate normal distribution was derived on $(\alpha, \log\beta)$ that stochastically gives the best fit to the 2.5%, 50%, and 97.5% quantiles of the prior probability of DLT at each dose. The parameters $(\alpha, \log\beta)$ have a bivariate normal distribution with mean= $(-1.09, 0.26)$, standard deviation= $(2.17, 0.51)$, and $\rho=-0.89$.

Simulation Studies

We performed simulations under different scenarios of possible dose-toxicity relationships to investigate the operational characteristics of the toxicity band versus traditional 3+3 design:

- 3-patient cohorts starting from 20 mg.
- Maximum number of patients: 15 for toxicity-band method, and 15 for traditional 3+3 method.
- Rules for stopping early for toxicity-band method: at least 6 patients have been treated at or near MTD or the probability of dose being in target band greater than 0.5 or at least 9 patients have been accrued.

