As a conclusion, based on the simulation studies on a variety of scenarios and the illustrative examples, the toxicity-band method is slightly more aggressive than the traditional 3+3 design, and therefore provides a lower underdosing rate and a higher MTD selection rate, with a well-controlled overdosing rate at a prespecified criterion. Therefore, the modified 3+3 method that incorporates the principles of the toxicity-band method will be used in this study rather than the traditional 3+3 escalation paradigm.

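### With nine DLT-free patients at 20 and 30 mg, 3 DLTs in 6 patients at 40 mg pass the 0.25 overdose rule and make 40 mg the model's MTD; the simulations contain no curve steep enough to test this

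*Protocol*

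**What the plan says.** Protocol Attachment 9 uses a two-parameter logistic model with reference dose 40 mg and a bivariate normal prior on the intercept and log slope. The prior is fitted to a minimally informative Beta at each dose, which is said to be done "so that the operating characteristics of the model are robust to the selected prior distribution of DLT". Overdosing means a DLT probability above 0.33. The dose step reads "Exclude the doses such that the posterior probabilities of overdosing are larger than 0.25 (overdosing control criteria", and among the doses left, the one most likely to lie in the 0.20 to 0.33 band is recommended. Section 7.2.2.2 stops the method at the maximum sample size or when "the recommended next dose level has been administered to at least 6 patients".

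The Attachment 9 summary, and Section 10.1 in the same terms, say the method selects the MTD more often than 3+3 "with a well-controlled overdosing rate at a prespecified criterion". The text under Table App.3 adds that DLT percentages stay under 0.25.

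Two other sections put a figure on an observed rate. Section 7.2.4 provides for a review "If the rate of DLT-equivalent toxicities is unacceptable", with more than 33% of patients at a dose level as its example. In Phase 1a that concerns Cycle 2 and later. Section 10.10 requires a Phase 1b data review at one-third or more in Cycle 1, once at least 6 patients are enrolled.

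**The concern.** The 0.25 rule is the only quantitative guard on overdosing in Phase 1a Cycle 1. The model lets clean cohorts at lower doses offset DLTs at 40 mg, so the question is how many DLTs at 40 mg can be offset before the rule excludes it. The protocol does not tabulate this. If half the patients treated at 40 mg can have a DLT and the rule still passes, the overdose-control claim needs qualifying.

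The MTD is the primary result of Phase 1a, and under Section 7.2.2 it is the dose carried into Phase 1b, planned at about 30 patients.

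**Working it through.** **Inputs (Attachment 9 unless stated).** logit p(d) = α + β·log(d/40). The prior on (α, log β) has mean (−1.09, 0.26), SD (2.17, 0.51) and correlation −0.89. Cohorts are of 3 from 20 mg, with at most 15 patients and steps of at most 10 mg (Section 6.2). The posterior is proportional to the prior times the product over doses of p(d)^x·(1−p(d))^(n−x), integrated on a grid.

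Attachment 9 also lists a stop at 9 patients accrued. Read literally it would end every trial at 9, which does not fit the printed mean sizes of 13.2 to 14.5, so it is not applied.

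**Reproducing the plan's figures.** Prior medians at 10/20/30/40 mg come out at 0.052/0.119/0.187/0.252, against 0.06/0.12/0.18/0.26 in Table App.1. Against Table App.3, Scenarios 1 to 4, with a 10-mg level allowed:

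| | Computed, 6-patient stop | Computed, no early stop | Printed |
|---|---|---|---|
| 40 mg selected | 0.686/0.524/0.369/0.226 | 0.715/0.548/0.383/0.232 | 0.689/0.546/0.374/0.222 |
| Mean N | 12.4/12.0/11.6/11.2 | 14.4/14.0/13.6/13.2 | 14.5/14.1/13.6/13.2 |

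The reproduction is close but incomplete: the trial-wide DLT rate without the early stop is 0.149 in Scenario 1 and 0.233 in Scenario 4, against 0.164 and 0.270 printed.

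**3/6 DLTs at 40 mg, by lower-dose data.**

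| 20 mg | 30 mg | P(p(40) > 0.33) | 0.25 rule |
|---|---|---|---|
| 0/3 | 0/6 | 0.197 | passes |
| 0/6 | 0/3 | 0.232 | passes |
| 0/3 | 0/3 | 0.341 | excluded |
| one DLT among 9 | | 0.41 to 0.48 | excluded |

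In the first row the target-band probabilities at 20/30/40 mg are 0.118/0.293/0.412, so 40 mg is recommended. It has 6 patients and N = 15. Other grids put the 0.197 anywhere up to about 0.21.

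**How it is reached.** Enumerating every path gives three that end in the first row (DLTs per cohort):
- 20:0, 30:0, 40:2, 30:0, 40:1
- 20:0, 30:0, 40:1, 40:2, 30:0
- 20:0, 30:0, 40:0, 40:3, 30:0

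On the first path, 40 mg is excluded after 2/3 (about 0.32) and re-admitted after three clean patients at 30 mg (about 0.17). On the other two it is excluded at N = 12 (0.341) and re-admitted by the last cohort. The paths are the same with or without the 6-patient stop.

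**Frequency.** The three paths contain 9 + 9 + 1 = 19 patient orderings of 3 DLTs in 6, so the probability is 19·(1−p20)³·(1−p30)⁶·[p40(1−p40)]³. For Scenario 4 this is 19 × 0.82³ × 0.71⁶ × (0.42 × 0.58)³ = 0.019.

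| DLT rates at 20/30/40 mg | Probability |
|---|---|
| Scenario 1: 0.09/0.14/0.22 | 2.9% |
| Scenario 2: 0.12/0.19/0.27 | 2.8% |
| Scenario 3: 0.15/0.24/0.33 | 2.4% |
| Scenario 4: 0.18/0.29/0.42 | 1.9% |
| Assumed: 0.05/0.20/0.55 | 6.5% |
| Assumed: 0.05/0.15/0.60 | 8.5% |

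Under the two assumed curves, with levels 20, 30 and 40 mg only, 40 mg is named in about 20% of trials. This end state accounts for 31% and 42% of those selections.

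**Scenario coverage.** Attachment 9 says steep curves raise the overdosing concern and that the simulations assess it. The steepest scenario rises only from 0.18 to 0.42 between 20 and 40 mg. In Scenarios 1 to 3 the true MTD is the top dose, so selection above it cannot occur. Scenario 4 alone can show it: 0.222 for the toxicity-band method against 0.127 for 3+3.

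**Robustness to the prior.** Because the reference dose is 40 mg, α is the logit DLT rate at 40 mg, and changing the prior correlation leaves the 40-mg marginal prior untouched. Setting the correlation to 0 with the printed SDs gives about 0.29 for the same data, so 40 mg would be excluded. The decision for this outcome turns on the joint prior, and Attachment 9 simulates no alternative prior.

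**The case against.** A reader might infer that 3/6 at 40 mg passes in general. It does not: direct escalation through six clean patients gives 0.341 and the model steps down, and any lower-dose DLT also excludes 40 mg.

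A reader might also blame the prior for pulling the probability down from what 40 mg alone would show. With 3/6 at 40 mg and no other data, the joint prior gives 0.755. The fall to 0.20 therefore comes from nine DLT-free patients on a rising curve, and using all the DLT data is the stated purpose of the method. Nor is the prior correlation of 0.993 between the 20- and 40-mg logits strong evidence by itself. It reflects mainly the wide intercept SD and is still 0.97 when the parameter correlation is 0. Prior correlation affects how much is borrowed, but is not the main cause.

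The safeguards are real:
- Attachment 9 lets the decision makers depart from the model.
- Section 7.2.2.2 has the team weigh the observed DLT rate and document agreement before escalating.
- Section 10.10 adds cohort reviews and an interim analysis before Phase 1b.
- Section 10.1 allows the MTD to be revised on Phase 1b data.

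The end state is uncommon under the plan's own scenarios, and Attachment 9 openly calls the method slightly more aggressive than 3+3. The more-than-33% figure in Section 7.2.4 is only an example, and it leads to review rather than exclusion.

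These points limit the concern but do not answer it. The safeguards set no figure for Phase 1a Cycle 1, and the overdose-control claim is made for the model, not for the committee.

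**Conclusion.** The concern holds in this conditional form. Under the printed prior and rules, 0/3, 0/6 and 3/6 at 20, 30 and 40 mg make 40 mg the model's MTD, with an overdose probability of about 0.20. The probability of this is 1.9 to 2.9% under Table App.2, and 6.5 and 8.5% under two curves that are assumptions and do not come from the protocol. These figures assume the model is followed, cohorts of exactly 3, and N = 15.

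The documents do not support the stronger reading that the protocol commits Phase 1b to such a dose, because people decide and later reviews exist. What is unsupported is the wording. No printed simulation covers a steep curve, and nothing printed shows robustness to the prior. The statement that DLT percentages stay under 0.25 conflicts with the 0.270 printed for the toxicity-band method in Scenario 4. It also sets a DLT rate against a limit defined for a posterior probability. The point should be addressed, but it does not invalidate the design.

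**What to change.** 1. Reconcile the MTD-declaration step (Section 7.2.2.2 and the dose-recommendation rules in Attachment 9) with Sections 7.2.4 and 10.10, so that the protocol says how an observed Cycle 1 DLT rate in Phase 1a relates to the figures used there. Which rule applies is for the sponsor and investigators. Keep SAP Section 6.15 in step, since it repeats the Phase 1b trigger with an added two-event exception.
2. Tabulate the model's recommendation for each reachable outcome at 30 and 40 mg, so that the team sees in advance when 40 mg is re-admitted.
3. Add at least one steep scenario, with the true MTD below 40 mg, to Tables App.2 and App.3.
4. Restate the well-controlled overdosing claim (Attachment 9 and Section 10.1), the statement about DLT percentages and 0.25, and the claim of robustness to the prior.

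The prior need not be refitted for this. The cost is a re-run of the simulations, some text, and a less favourable description of the design.

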Attachment 10. Protocol CXAD RECIST Version 1.1

Response and progression will be evaluated in this study using the international criteria proposed by the New Response Evaluation Criteria in Solid Tumours (RECIST): Revised RECIST Guideline (version 1.1; Eisenhauer et al. 2009).

Measurability of Tumor at Baseline

Tumor lesions/lymph nodes will be categorized at baseline as measurable or nonmeasurable. Measurable disease is defined by the presence of at least 1 measurable lesion.

Measurable

Tumor lesions: Measured in at least 1 dimension (longest diameter in the plane of measurement is to be recorded) with a minimum size of:

- 10 mm by CT or MRI scan (slice thickness ≤ 5 mm)
- 10-mm calliper measurement by clinical examination (nonmeasurable lesions if cannot be accurately measured with callipers)
- 20 mm by chest x-ray.

Malignant lymph nodes: To be considered pathologically enlarged and measurable, a lymph node must be ≥ 15 mm in short axis when assessed by CT scan (CT scan thickness recommended to be ≤ 5 mm).

Nonmeasurable

All other lesions, including small lesions (longest diameter < 10 -mm or pathological lymph nodes with ≥ 10 - to < 15 -mm short axis) as well as truly nonmeasurable lesions. Lesions considered truly nonmeasurable include: leptomeningeal disease, ascites, pleural/pericardial effusions, lymphangitis cutis/pulmonis, inflammatory breast disease, lymphangitis involvement of skin or lung, abdominal masses/abdominal organomegaly identified by physical examination that is not measurable by reproducible imaging techniques.

Special Considerations for Lesion Measurability**Bone Lesions:**

- Bone scan, PET scan, or plain films are not considered adequate imaging techniques to measure bone lesions.
- Lytic bone lesions or mixed lytic-blastic lesions, with identifiable soft tissue components, that can be evaluated by cross sectional imaging techniques such as CT or MRI, can be considered measurable lesions if the soft tissue component meets the definition of measurability.
- Blastic bone lesions are nonmeasurable.

Cystic lesions:

- Simple cysts should not be considered as malignant lesions (neither measurable nor nonmeasurable)
- Cystic lesions thought to represent cystic metastases can be considered as measurable lesions, if they meet the definition of measurability. If noncystic lesions are presented in the same patients, these are preferred for selection as target lesions.

Lesions with Prior Local Treatment:

- Tumor lesions situated at a previously irradiated area, or in an area subjected to other loco-regional therapy, are nonmeasurable unless there has been demonstrated progression in the lesion.

Baseline Documentation of Target and Nontarget Lesion***Target Lesions***

When more than 1 measurable lesion is present at baseline, all lesions up to a maximum of 5 lesions total (and a maximum of 2 lesions per organ), representative of all involved organs, should be identified as target lesions and will be recorded and measured at baseline. Nonnodal target lesions should be selected on the basis of their size (lesions with the longest diameter), be representative of all involved organs, and should be able to be reproduced in repeated measurements. Measurable lymph nodes are target lesions if they meet the criteria of a short axis of ≥ 15 mm by CT scan. All measurements are to be recorded in the CRF in millimeters (or decimal fractions of centimeters [cm]).

Nontarget Lesions

All other lesions (or sites of disease) are identified as nontarget lesions (chosen based on their representativeness of involved organs and the ability to be reproduced in repeated measurements) and should be recorded at baseline. Measurement of these lesions are not required but should be followed as “present,” “absent,” or in rare cases “unequivocal progression.” In addition, it is possible to record multiple nontarget lesions involving the same organ as a single item on the CRF (for example, multiple liver metastases recorded as 1 liver lesion).

Lymph nodes with short axis ≥ 10 mm but < 15 mm should be considered nontarget lesions. Nodes that have a short axis < 10 mm are considered nonpathological and are not recorded or followed.

Specifications by Methods of Measurement

All measurements should be recorded in metric notation, using a ruler or callipers if clinically assessed. All baseline evaluations should be performed as closely as possible to the beginning of treatment and never more than 4 weeks before the beginning of the treatment.

The same method of assessment and the same technique should be used to characterize each identified and reported lesion at baseline and during follow-up. Imaging-based evaluation

should always be done rather than clinical examination unless the lesion(s) being followed cannot be imaged but are able to be assessed by clinical examination.

An adequate volume of a suitable contrast agent should be given so that the metastases are demonstrated to best effect and a consistent method is used on subsequent examinations for any given patient. If prior to enrolment it is known a patient is not able to undergo CT scans with IV contrast due to allergy or renal insufficiency, the decision as to whether a noncontrast CT or MRI (with or without IV contrast) should be used to evaluate the patient at baseline and follow-up should be guided by the tumor type under investigation and the anatomic location of the disease.

Clinical Lesions: Clinical lesions will only be considered measurable when they are superficial and ≥ 10 -mm diameter as assessed using callipers (for example, skin nodules). For the case of skin lesions, documentation by color photography, including a ruler to estimate the size of the lesion is recommended. When lesions can be evaluated by both clinical examination and imaging, imaging evaluation should be undertaken since it is more objective and may be reviewed at the end of the study.

Chest X-Ray: Chest CT is preferred over chest x-ray when progression is an important endpoint. Lesions on chest x-ray may be considered measurable if they are clearly defined and surrounded by aerated lung.

CT and MRI: CT scan is the best currently available and reproducible method to measure lesions selected for response assessment. Measurability of lesions on CT scan is based on the assumption that CT slice thickness is ≤ 5 mm. When CT scan have slice thickness > 5 mm, the minimum size for a measurable lesion should be twice the slice thickness. MRI is also acceptable in certain situations (for example, for body scans). If there is concern about radiation exposure from CT, MRI may be used instead of CT in selected instances.

Ultrasound: Ultrasound should not be used to measure lesion size. Ultrasound examinations cannot be reproduced in their entirety for independent review at a later date and, because they are operator-dependent, it cannot be guaranteed that the same technique and measurements will be taken from 1 assessment to the next. If new lesions are identified by ultrasound in the course of the study, confirmation by CT or MRI is advised.

Endoscopy, Laparoscopy: The utilization of these techniques for objective tumor evaluation is not advised. However, such techniques can be useful to confirm complete pathological response when biopsies are obtained or to determine relapse in trials where recurrence following CR or surgical resection is an endpoint.

Tumor Markers: Tumor markers alone cannot be used to assess tumor response. If markers are initially above the upper normal limit, they must normalize for a patient to be considered in CR. Specific guidelines for both prostate-specific antigen response (in recurrent prostate cancer) and CA-125 response (in recurrent ovarian cancer) have been published.

Cytology, Histology: These techniques can be used to differentiate between PR and CR in rare cases if required by protocol (for example, residual lesions in tumor types such as germ cell tumors, where known residual benign tumors can remain). When effusions are known to be a

potential adverse effect of treatment (for example, with certain taxane compounds or angiogenesis inhibitors), the cytological confirmation of the neoplastic origin of any effusion that appears or worsens during treatment can be considered if the measurable tumor has met criteria for response or SD in order to differentiate between response (or SD) and PD.

PET Scan (FDG-PET, PET CT): PET is not recommended for lesion assessment. If a new lesion is found by PET, another assessment must be done by CT, unless the PET CT is of diagnostic quality. If CT is done to confirm the results of the earlier PET scan, the date of progression must be reported as the earlier date of the PET scan.

Bone Scan: If lesions measured by bone scan are reported at baseline, it is necessary to repeat the bone scan when trying to identify a CR or PR in target disease or when progression in bone is suspected.

Response Criteria

Evaluation of Target Lesions

CR: Disappearance of all target lesions. Any pathological lymph nodes (whether target or nontarget) must have reduction in short axis to <10 mm. Tumor marker results must have normalized.

PR: At least a 30% decrease in the sum of diameter of target lesions, taking as reference the baseline sum diameters.

PD: At least a 20% increase in the sum of the diameters of target lesions, taking as reference the smallest sum on study (including the baseline sum if that is the smallest). In addition to the relative increase of 20%, the sum must also demonstrate an absolute increase of at least 5 mm. The appearance of 1 or more new lesions is also considered progression.

For equivocal findings of progression (for example, very small and uncertain new lesions; cystic changes or necrosis in existing lesions), treatment may continue until the next scheduled assessment. If at the next scheduled assessment, progression is confirmed, the date of progression should be the earlier date when progression was suspected.

SD: Neither sufficient shrinkage to qualify for PR, nor sufficient increase to qualify for PD, taking as reference the smallest sum diameters while on study.

Not Evaluable: When an incomplete radiologic assessment of target lesions is performed or there is a change in the method of measurement from baseline that impacts the ability to make a reliable evaluation of response.

Evaluation of Nontarget Lesions

Complete Response (CR): Disappearance of all nontarget lesions and normalization of tumor marker level. All lymph nodes must be nonpathological or normal in size (<10-mm short axis).

Non-CR/Non-PD: Persistence of 1 or more nontarget lesions and/or maintenance of tumor marker level above the normal limits.

PD: Unequivocal progression of existing nontarget lesions. The appearance of 1 or more new lesions is also considered progression.

Not Evaluable: When a change in method of measurement from baseline occurs and impacts the ability to make a reliable evaluation of response.

Evaluation of Best Overall Response

The best overall response is the best response recorded from the start of the study treatment until the earliest of objective progression or start of new anticancer therapy, taking into account any requirement for confirmation. The patient's best overall response assignment will depend on the findings of both target and nontarget disease and will also take into consideration the appearance of new lesions. The best overall response will be calculated via an algorithm using the assessment responses provided by the investigator over the course of the trial.

Time Point Response

It is assumed that at each protocol-specified time point, a response assessment occurs. (When no imaging/measurement is conducted/made at all at a particular time point, the patient is not evaluable (NE) at that time point.) Table App.4 provides a summary of the overall response status calculation at each time point for patients who have *measurable disease* at baseline.

Table App.4. Time Point Response: Patients with Target (\pm Nontarget) Disease

Target Lesions	Nontarget Lesions	New Lesions	Overall Response
CR	CR	No	CR
CR	Non-CR/non-PD	No	PR
CR	Not evaluated	No	PR
PR	Non-PD or not all evaluated	No	PR
SD	Non-PD or not all evaluated	No	SD
Not all evaluated	Non-PD	No	NE
PD	Any	Yes or No	PD
Any	PD	Yes or No	PD
Any	Any	Yes	PD

Abbreviations: CR = complete response; PR = partial response; SD = stable disease; PD = progressive disease; NE = not evaluable.

Table App.5 is to be used when patients have *nonmeasurable* disease only.

Table App.5. Time Point Response: Patients with Nontarget Disease Only

Nontarget Lesions	New Lesions	Overall Response
CR	No	CR
Non-CR/non-PD	No	Non-CR/non-PD ^a
Not all evaluated	No	NE
Unequivocal PD	Yes or No	PD
Any	Yes	PD

Abbreviations: CR = complete response; PD = progressive disease; NE = not evaluable.

^a non-CR/non-PD is preferred over SD for nontarget disease.

Frequency of Tumor Re-Evaluation

A baseline tumor evaluation must be performed within 4 weeks before patient begins study treatment. Frequency of tumor re-evaluation while on and adapted to treatment should be protocol-specific and adapted to the type and schedule of treatment. In the context of Phase 2 studies where the beneficial effect therapy is not known, follow-up every 6 to 8 weeks is reasonable. Normally, all target and nontarget sites are evaluated at each assessment using the same method. However, bone scans may need to be repeated only when CR is identified in target disease or when progression in bone is suspected.

Confirmatory Measurement/Duration of Response

Confirmation:

The main goal of confirmation of objective response in clinical trials is to avoid overestimating the response rate observed. The confirmation of response is particularly important in *nonrandomized trials* where response (CR/PR) is the primary end point. In this setting, to be assigned a status of PR/CR, changes in tumor measurements must be confirmed by repeat assessments that should be performed no less than 4 weeks after the criteria for response are first met. To confirm a response of CR, a full assessment of all target and nontarget lesions that were present at baseline must occur, including those measured by bone scan. To confirm a PR or SD, a full assessment of target lesions that were present at baseline must occur; assessment of nontarget lesions is not required.

However, in *randomized trial* (Phase 2 or 3) or studies where SD or progression is the primary endpoints, confirmation of response is not required. But, elimination of the requirement may increase the importance of central review to protect against bias, in particular of studies which are not blinded.

In the case of SD, follow-up measurements must have met the SD criteria at least once after start of treatment at a minimum interval not less than 6 weeks measured from first dose.

Duration of Overall Response

The duration of overall response is measured from the time measurement criteria are first met for CR or PR (whichever is first recorded) until the first date that disease is recurrent or objective progression is observed (taking as reference for PD the smallest measurements recorded on study).

The duration of overall CR is measured from the time measurement criteria are first met for CR until the first date that recurrent disease is objectively documented.

Duration of Stable Disease

Stable disease is measured from the start of the treatment (in randomized trials, from date of randomization) until the criteria for objective progression are met, taking as reference the smallest sum on study (if the baseline sum is the smallest, that is the reference for calculation of PD).

Independent Review of Response and Progression

When objective response (CR + PR) is the primary end point, and when key drug development decisions are based on the observation of a minimum number of responders, it is recommended that all claimed responses be reviewed by an expert(s) independent of the study. If the study is a randomized trial, ideally reviewers should be blinded to treatment assignment.

**Attachment 11. Protocol CXAD Durvalumab Monotherapy
Dosing Modification and Toxicity Management Guidelines
for Immune-Mediated, Infusion-Related, and Non-Immune-
Mediated Reactions**

Pneumonitis

AEs of pneumonitis are of interest as pneumonitis has been reported with anti-PD-1 mAbs (Topalian et al. 2012). Initial work-up should include high-resolution CT scan, ruling out infection, and pulse oximetry. Pulmonary consultation is highly recommended.

Guidelines for the management of patients with immune-mediated events including pneumonitis are outlined in the table below.

Infusion-Related Reactions

All infusion-related reactions occurring from the start of durvalumab infusion up to 48 hours after the infusion start time are considered AESIs. All infusion reactions are to be considered SAEs and should be reported as per the SAE reporting guidelines described in Section 8.1.2.6.

Based on the mechanism of action of durvalumab leading to T-cell activation and proliferation, there is the possibility of observing immune-related AEs during the conduct of this study. Potential immune-related AEs include immune-mediated enterocolitis, dermatitis, hepatitis, and endocrinopathies. Patients should be monitored for signs and symptoms of immune-related AEs. In the absence of an alternative etiology (eg, infection or PD) signs or symptoms of enterocolitis, dermatitis, hepatitis, and endocrinopathy should be considered to be immune-related.

All AEs of possible infusion reactions are to be reported as IRRs, if occurring from the start of durvalumab infusion up to 48 hours after the infusion start time.

Hypersensitivity Reactions

Hypersensitivity reactions as well as infusion-related reactions have been reported with anti-PD-L1 and anti-PD-1 therapy (Brahmer et al. 2012). As with the administration of any foreign protein and/or other biologic agents, reactions following the infusion of mAbs can be caused by various mechanisms, including acute anaphylactic (immunoglobulin E-mediated) and anaphylactoid reactions against the mAb, and serum sickness. Acute allergic reactions may occur, may be severe, and may result in death. Acute allergic reactions may include hypotension, dyspnea, cyanosis, respiratory failure, urticaria, pruritus, angioedema, hypotonia, arthralgia, bronchospasm, wheeze, cough, dizziness, fatigue, headache, hypertension, myalgia, vomiting and unresponsiveness.

Guidelines for management of patients with hypersensitivity (including anaphylactic reaction) and infusion-related reactions are outlined in the table below.

Hepatic Function Abnormalities (Hepatotoxicity)

Increased transaminases have been reported during treatment with anti-PD-L1/anti-PD-1 antibodies (Brahmer et al. 2012). Inflammatory hepatitis has been reported in 3% to 9% of patients treated with anti-CTLA-4 monoclonal antibodies (eg, ipilimumab). The clinical manifestations of ipilimumab-treated patients included general weakness, fatigue, nausea and/or mild fever and increased liver function tests such as AST, ALT, alkaline phosphatase, and/or total bilirubin.

Hepatic function abnormality is defined as any increase in ALT or AST to greater than 3x ULN and concurrent increase in total bilirubin to be greater than 2x ULN. Concurrent findings are those that derive from a single blood draw or from separate blood draws taken within 8 days of each other. Follow-up investigations and inquiries will be initiated promptly by the investigational site to determine whether the findings are reproducible and/or whether there is objective evidence that clearly supports causation by a disease (eg, cholelithiasis and bile duct obstruction with distended gallbladder) or an agent other than the investigational product. Guidelines for management of patients with hepatic function abnormality are outlined in the table below.

Cases where a patient shows an AST or ALT $\geq 3x$ ULN or total bilirubin $\geq 2x$ ULN may need to be reported as SAEs. These cases should be reported as SAEs if, after evaluation they meet the criteria for a Hy's Law case or if any of the individual liver test parameters fulfill any of the SAE criteria.

Criteria for Hy's Law (FDA 2009)

- The drug causes hepatocellular injury, generally shown by a higher incidence of 3-fold or greater elevations above the ULN of ALT or AST than the (nonhepatotoxic) control drug or placebo
- Among study patients showing such aminotransferase elevations, often with aminotransferases much $>3x$ ULN, one or more also show elevation of serum total bilirubin to $>2x$ ULN, without initial findings of cholestasis (elevated serum alkaline phosphatase)
- No other reason can be found to explain the combination of increased aminotransferases and total bilirubin, such as viral hepatitis A, B, or C; preexisting or acute liver disease; or another drug capable of causing the observed injury.

Hepatic function abnormality

